#### Notes:

1. In Poland, the HCP guide and HCP checklist are present in one document.

2. In countries with available information, the date of distribution will be considered, otherwise we will consider 6 months from the date of approval of the EMs. The approval and distribution dates might be varied for different MAHs in one country; therefore, we have referred to the latest date for the approval and distribution per country in this table.

Template No.: RWI\_TP\_EPI0016 Revision 1 Reference: RWI\_WI\_EPI0005

Effective Date: 15Jun2018

Copyright © 2018 IQVIA. All rights reserved. The contents of this document are confidential and proprietary to IQVIA Holdings Inc. and its subsidiaries. Unauthorized use, disclosure or reproduction is strictly prohibited.

Impact of EU label changes on methotrexate for weekly administration

Version 2.0 dated 21 February 2022

Protocol/Study No: SC02 EMA/2018/19/PE Page **23** of **92** 

As a result of these data the following measures were introduced for all oral and parenteral MTX formulations with at least one indication requiring once-weekly dosing (e.g. rheumatologic/dermatological diseases or Crohn's disease):

- Update of summary of product characteristics (SmPC) section 4.2:
  - Only physicians with expertise in the use of MTX and understanding of the risks related to MTX therapy should prescribe MTX;
  - The recommendation to divide the dose has been removed (also package leaflet section 3);
  - Boxed warning that the product must only be taken/used once-weekly (also package leaflet section 3);
  - o Prescribers should ensure that patients or their caregivers will be able to comply with the once-weekly regimen (for oral MTX products only).
- Visual reminder on the outer packaging to take/use the product only once a week
  with space to mark a weekday for intake/use; for MTX-containing products with at
  least one indication requiring treatment once a week and an oncologic indication the
  visual reminder must also include the once-weekly indication
- Visual reminder on the inner packaging that the product must only be taken/used
  once-weekly; for MTX-containing products with at least one indication requiring
  treatment once a week and an oncologic indication the visual reminder must also
  include the once-weekly indication
- Switch from bottle to blister packaging (only oral MTX formulations and over a transition period of 4 years)
- Patient card (only oral MTX formulations) with information on once-weekly dosing regimen and space to write the day of the week
- Update of existing EMs for healthcare professionals (HCPs) (i.e. checklist or guide) (only oral MTX formulations)
- Direct healthcare professional communication (DHPC)

# 8. RESEARCH QUESTION AND OBJECTIVES

The aim of the current study is to examine the effectiveness of product-specific risk-minimisation measures for MTX, by carrying out a survey to evaluate the impact of European union (EU) label changes for medicinal products containing MTX for weekly administration, with reference to the 2019 referral procedure (refer Section 7.2).

The primary objectives of the study are:

Template No.: RWI\_TP\_EPI0016 Revision 1 Reference: RWI\_WI\_EPI0005

Protocol/Study No: SC02 EMA/2018/19/PE

Page 24 of 92

- To determine the extent of prescriber awareness and knowledge of the risk of inadvertent overdose due to daily instead of weekly use and adherence to SmPC recommendations for oral and parenteral MTX-containing medicines with at least one indication requiring once-weekly dosing, with particular focus on the following elements:
  - 1.1. Receipt and awareness of the DHPC
  - 1.2. Knowledge of the dosing frequency of MTX in the treatment of inflammatory diseases (e.g. rheumatologic/dermatological diseases or Crohn's disease), by indication
  - 1.3. Knowledge of the updated posology instructions and boxed warning
  - 1.4. Receipt and awareness of the new or updated EMs for HCPs (checklist or guide) and awareness of the patient card to avoid the risk of inadvertent overdose due to daily instead of weekly use
- 2. To determine the extent of pharmacist awareness and knowledge of the patient card, the visual reminder on the outer packaging and the need to mark the day of intake for indications requiring once-weekly dosing regimens, and adherence to marking the day of intake on the outer packaging
- 3. To determine the extent of patient awareness and knowledge of the following elements introduced to avoid incorrect administration schedules for oral and parenteral MTX-containing medicines with at least one indication requiring once-weekly dosing:
  - 3.1. Receipt and awareness of the patient card, and knowledge of symptoms of MTX overdose and the purpose of the patient card (i.e. to note the day of intake for indications requiring once-weekly dosing regimens, and steps to be taken if symptoms arise, and to alert any HCP not familiar with MTX treatment about the once-weekly dosing regimen e.g. on hospital admission, change of care etc.)
  - 3.2. Knowledge of the once-weekly dosing frequency of MTX in the treatment of inflammatory diseases (e.g. rheumatologic/dermatological diseases or Crohn's disease), for his/her indication
  - 3.3. a) Awareness and knowledge of the visual reminder on the packaging of oral and parenteral MTX-containing products; b) Awareness and knowledge of the boxed warning in the package leaflet.

#### 9. RESEARCH METHODS

Template No.: RWI\_TP\_EPI0016 Revision 1 Reference: RWI\_WI\_EPI0005

Protocol/Study No: SC02 EMA/2018/19/PE

Page 25 of 92

# 9.1 Study Design

This study is a cross-sectional, multinational, and multichannel survey based on primary data collection conducted among prescribers, pharmacists and patients in 5 selected European countries (France, Germany, Greece, Poland, and Sweden), where there are a sufficient number of eligible prescribers, pharmacist and patients with MTX experience. The survey is designed to examine the impact of EU label changes for medicinal products containing MTX for weekly administration.

#### 9.1.1 Study Period

The data collection period will last about 12 weeks in each country for prescribers, pharmacists and patients surveys. The fieldwork in each country will only start after the EMs have been distributed in each country to enable the assessment of EM effectiveness. Generally, a 6 to 12-month period is considered after the distribution of the EM to allow for full implementation of the risk-minimisation measures (RMMs). Accordingly, the survey start date will begin approximately 18 to 24 months after the date of distribution of the EM in the individual countries listed for evaluation within this protocol. This date may vary by country, based on the date of EM approval by the local Health Authority. The survey will be conducted in outpatient settings through a web questionnaire. To ensure that the invitation and survey are comprehensible, all outreach will be conducted in the local language of each country.

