#### **Milestones**

Anticipated start of data collection: 01 January 2022
Date(s) of study progress reports: Not Applicable
Interim report(s) of study results: Not Applicable

Registration in the EU PAS register: 23 December 2021

Study report: 11 September 2022 Manuscript: 11 November 2022

Template No.: RWI\_TP\_EPI0016 Revision 1 Reference: RWI\_WI\_EPI0005

Impact of EU label changes on methotrexate for weekly administration

Version 2.0 dated 21 February 2022

Protocol/Study No: SC02 EMA/2018/19/PE

Page 17 of 92

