# 6. MILESTONES

The planned dates for key study milestones are:

Milestone	Planned date	Comment
Start of data collection	01 January 2022	Subject to timeline of protocol approval
End of data collection	30 April 2022	
Registration in the EU PAS register	Around one month after the protocol approval	23 December 2021
Study report	11 September 2022	
Manuscript	11 November 2022	

Template No.: RWI\_TP\_EPI0016 Revision 1 Reference: RWI\_WI\_EPI0005

Protocol/Study No: SC02 EMA/2018/19/PE

Page 19 of 92

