# Table 1 Educational Materials' and Labels' Approval and Dissemination dates

RMM	France	Germany	Greece	Poland*	Sweden
Updated SmPC with boxed warning					
Approved date	04 Nov 2020	11 Nov 2020	10 Jun 2021	-	23 Mar 2020
Distributed date	6 months after approval	6 months after approval	6 months after approval	11 Sep 2020	6 months after approval
Updated PIL with boxed warning					
Approved date	04 Nov 2020	11 Nov 2020	10 Jun 2021	-	23 Mar 2020
Distributed date	6 months after approval	6 months after approval	6 months after approval	11 Sep 2020	6 months after approval
Visual reminder inner packaging					
Approved date	04 Nov 2020	11 Nov 2020	10 Jun 2021	-	23 Mar 2020
Distributed date	6 months after approval	6 months after approval	6 months after approval	11 Sep 2020	6 months after approval
Visual reminder outer packaging					
Approved date	04 Nov 2020	11 Nov 2020	10 Jun 2021	-	23 Mar 2020
Distributed date	6 months after approval	6 months after approval	6 months after approval	11 Sep 2020	6 months after approval
Patient card with space for weekday	·				

Template No.: RWI\_TP\_EPI0016 Revision 1 Reference: RWI\_WI\_EPI0005

Effective Date: 15Jun2018

Copyright © 2018 IQVIA. All rights reserved. The contents of this document are confidential and proprietary to IQVIA Holdings Inc. and its subsidiaries. Unauthorized use, disclosure or reproduction is strictly prohibited.

Protocol/Study No: SC02 EMA/2018/19/PE

Page 22 of 92

RMM	France	Germany	Greece	Poland*	Sweden
Approved date	-	-	-	24 Mar 2020	22 Jan 2020
Distributed date	16 Dec 2020	25 Nov 2019	Soon to be completed	6 months after approval	6 months after approval
HCP checklist					
Approved date	Not Applicable	-	Not Applicable	10 Jun 2020	22 Jan 2020
Distributed date	Not Applicable	18 Mar 2020	Not Applicable	1 month after approval	6 months after approval
HCP guide					
Approved date	18 Mar 2021	Not Applicable	May 2020	10 Jun 2020	22 Jan 2020
Distributed date	6 months after approval	Not Applicable	July 2020	1 month after approval	6 months after approval
DHCP					
Approved date	-	-	17 Sep 2019	18 Dec 2019	23 Sep 2019
Distributed date	09 Apr 2020	25 Nov 2019	27 Nov 2019	6 months after approval	6 months after approval

\*Dates of submission for regulatory approval

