# 5.3 Assessment of Success (Patient questionnaire)

Objectives	Questions	Is the question included in the assessment of success? (Yes/No)	Definition of correctly answered question	Assessment of success
	Q1. Please select the option that best describes your experience with the [patient card: name in the local language] (only for oral methotrexate formulations)?	Yes	Question completed correctly [Answer '1' or '2' is desirable]	A patient is successful for awareness when he/she receives the patient card, and is aware of the
	Q2. How did you obtain the information regarding the existence of the [patient card: name in the local language] (only for oral formulations)?	No; complementary information on source of patient card		
Receipt and Awareness (6 questions)	Q3. Please select the option that best describes your experience with the methotrexate package leaflet	Yes	Question completed correctly [Answer '1'is desirable]	boxed warining in the packaging leaflet and visual reminder on the outer packaging (desirable answers).
	Q4. How did you obtain the information regarding the existence of the boxed warning on the methotrexate package leaflet?	No; complementary information on source of package leaflet knowledge		Success for awareness if ≥80% of patients are successful.
	Q5. Please select the option that best describes your experience with the methotrexate outer packaging of oral and parenteral methotrexate-containing products	Yes	Question completed correctly [Answer '1'is desirable]	

Template No.: RWI\_TP\_EPI0016 Revision 1 Reference: RWI\_WI\_EPI0005

Effective Date: 15Jun2018

Page 90 of 92

	Q6. How did you obtain the information regarding the existence of the visual reminder on when to use/take methotrexate?	No; complementary information on source of visual reminder on the outer packaging		
	Q7. According to your knowledge about the purpose of the [patient card: name in the local language] (only for oral methotrexate formulations), please indicate if you agree or disagree with the following statements	Yes	Question completed correctly (6 sub-questions [3 False and 3 True])	A patient is successful for knowledge when he/she scores at least 20 out of 25 points (80%) for questions, including sub-questions, which are completed with correct/desiable answers.  Success for knowledge if ≥ 80% of patients are successful.

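### The protocol's own dates do not give the stated 18 to 24 months between distribution and survey for the French HCP guide or the Greek patient card, and Annex 5 scores these items without exemption

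*Protocol*

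**What the plan says.** Section 9.1.1 makes three statements about timing.

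- Distribution comes first: "The fieldwork in each country will only start after the EMs have been distributed in each country".
- On implementation: "Generally, a 6 to 12-month period is considered after the distribution of the EM to allow for full implementation".
- On the resulting start: "Accordingly, the survey start date will begin approximately 18 to 24 months after the date of distribution of the EM in the individual countries". The section adds that the date may differ by country.

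The milestones in section 6 give one start for all five countries, "01 January 2022", subject to protocol approval, and an end on 30 April 2022. The current version is dated 21 February 2022.

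Table 1 in section 7.2 gives approval and distribution dates. Note 2 says that a known distribution date is used, otherwise approval plus 6 months, and that the latest date across marketing authorisation holders is shown. For the Greek patient card the entry is "Soon to be completed".

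Annex 5 sets the success rules. For patients: "A patient is successful for awareness when he/she receives the patient card, and is aware of the" boxed warning and the visual reminder. Pharmacists must be aware of the card and the visual reminder. Prescribers must have received the DHPC, guide and checklist and be aware of the card. Section 9.7.2.2 reads 80% successful respondents on each outcome as the mark of effectiveness.

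**The concern.** A survey of whether a measure worked needs respondents who have had time to meet it. Section 9.1.1 recognises this, but the calendar in the same document leaves some country-measure combinations with little or no time. Annex 5 has no rule for a measure that is recent or not yet distributed. A low Greek or French result on these items may therefore reflect lack of exposure, yet it enters the overall figure as evidence against the risk-minimisation measures. A reader who relies on the stated lag would not see this.

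**Working it through.** **Inputs.** Distribution dates are from Table 1, with approval plus 6 months where the table says so. Reference dates are 1 January 2022 (planned start), 21 February 2022 (version date) and 30 April 2022 (planned end). Lag in months = days / 30.4375.

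**Where the stated lag is reproduced.** At 1 January 2022 the DHPC stands at 18.5 (Poland), 20.8 (France), 21.3 (Sweden) and 25.2 months (Germany, Greece), and the German checklist at 21.5. The Polish and Swedish checklists and guides, the Greek guide (July 2020, day not given) and the Swedish card lie between 17.1 and 18.0, a fair reading of approximately 18. At 21 February, 7 of the 12 applicable card, checklist and guide entries fall within 18 to 24.

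**Where it is not.**

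| Item | Distribution date | 1 Jan 2022 | 21 Feb 2022 | 30 Apr 2022 |
|---|---|---|---|---|
| French HCP guide | 18 Mar 2021 + 6 months = 18 Sep 2021 | 105 days = 3.4 | 156 days = 5.1 | 224 days = 7.4 |
| Greek patient card | none given | – | – | – |
| Greek leaflet and packs (label items) | 10 Jun 2021 + 6 months = 10 Dec 2021 | 22 days = 0.7 | 73 days = 2.4 | 141 days = 4.6 |

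Counting from approval instead gives 9.5 months for the French guide and 6.7 for Greek labels at 1 January, still short of 18. The French guide passes 6 months on 18 March 2022, inside the window. Greek labels pass it on 10 June 2022, after the window closes.

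The French card (12.5 months at 1 January) and Polish card (15.2) are short of 18 but past the 6 to 12 month implementation period. The German card is at 25.2. Polish figures are uncertain because the table's footnote marks Polish dates as dates of submission.

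**How far the items reach in Annex 5.**

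- Patients: all three scored awareness items are card, leaflet and packaging. Of 25 knowledge points, 6 + 4 = 10 concern card and packaging, and 20 are needed.
- Pharmacists: both awareness items and all 6 + 4 = 10 knowledge points concern card and packaging. The one scored behaviour item concerns packaging.
- Prescribers: the guide is one of the items that must all be answered desirably.

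**Size in the extreme case**, with every Greek patient failing awareness:

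- Unweighted: Greece is 30/150 = 20% of the target sample. The ceiling is 120/150 = 80%, exactly the threshold.
- Weighted: the weights are not given. Assuming the Table 2 sales shares as weights, the five countries sum to 11.2 + 10.9 + 5.4 + 10.6 + 7.0 = 45.1 and Greece is 5.4/45.1 = 12%. The ceiling is 88%, and the other four countries would need 80/88 = about 91%.

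**The case against.** Several stronger readings are tempting, and the documents do not support them.

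- **That Greek packs at 0.7 months contradict the 18 to 24 months.** That interval runs from distribution of educational material. The list of measures in section 7.2 and the title of Table 1 separate labels from it, although the sentence introducing Table 1 blurs the two. The Greek label lag bears on the 6 to 12 month implementation period. French and German packs (8.0 and 7.7 months) meet that minimum.
- **That almost no educational-material entry fits.** This takes 1 January as exact and ignores that the lag is approximate.
- **That the protocol breaches its own distribution condition.** Applied as written, the condition holds Greece back. The defect is that the milestones give no separate Greek start. The Greek card entry may also mean that distribution is under way.
- **That overall success cannot exceed 80%.** Section 9.5.3 prefers weighted results, and Table 1 shows the latest date across holders, so some Greek patients may have had new packs earlier. For pharmacists the rule asks for awareness, not receipt, so a total Greek failure is less plausible still.
- **That these items are certain to be scored as failures.** This is inferred from the lack of an exemption in Annex 5. The questionnaires are separate documents and are not shown.

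It is also fair that results are reported by country, so a Greek shortfall would be visible, and that section 9.9.1 puts updated distribution information into the questionnaires. Neither changes the overall success rule. What stands is the mismatch for the French guide and Greek card, the short Greek label lag, and the absence of any rule for them.

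**Conclusion.** The point holds in limited form. The stated lag fails clearly for the French guide (3.4 to 7.4 months across the window) and cannot be shown for the Greek card. Greek leaflet and packs stay below the 6-month minimum throughout the window. No start date within that window repairs this: 18 months would be reached on 18 March 2023 for the French guide and on 10 June 2023 for Greek labels, after the planned report of 11 September 2022.

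The effect on the overall verdict is a possibility, not a forecast. The ceilings of 80% and about 88% assume that all Greek patients fail, and the second also assumes sales shares as weights. The dates rest on the protocol's approval-plus-6-months convention.

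**What to change.** 1. Replace the general 18 to 24 month statement in section 9.1.1 with the actual lag per measure and country, consistent with Table 1 and the milestones.
2. Give a separate Greek start date consistent with the distribution condition, or state that the condition is not met there.
3. Keep the planned success analysis. Fix country fieldwork start as the reference date for exposure, and pre-specify an additional overall success result. It omits the French guide item for prescribers, and omits Greece from the patient and pharmacist outcomes that depend on the card, leaflet or packaging. Report Greece separately.

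Dropping only the affected items in Greece would not work: Greek patients and pharmacists would have no scored awareness item left.

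The cost is wording and one extra set of results. The downside is that the additional result rests on four countries for those outcomes. By the section 9.5.1 formula at 50%, the margin goes from 1.96 × √(0.25/150) = 8.0 points to 1.96 × √(0.25/120) = 8.9 points, before weighting.

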# 9.2 Setting

The study will enrol prescribers, pharmacists and patients from France, Germany, Greece, Poland, and Sweden over an approximate 12-week time period. However, this time period can be extended if the target numbers are not achieved.

The 5 countries were selected based on the following criteria:

- Representativeness in term of largest MTX sales in Europe (Table 2)
- Representativeness in term of small and large countries
- Representativeness in term of different health care systems
- Representativeness in term of geographical spread across Western, Southern, Northern and Eastern European countries

As per European Medicines Agency (EMA) requirement, the study should be carried out in at least 5 European Economic Area (EEA)/EU countries.

Considering this requirement for diverse geographic representation of European countries, we applied an additional criterion of selection based on the use of MTX in European countries. In the selected countries there will be enough eligible prescribers, pharmacist and

Template No.: RWI\_TP\_EPI0016 Revision 1 Reference: RWI\_WI\_EPI0005

Impact of EU label changes on methotrexate for weekly administration

Version 2.0 dated 21 February 2022 Protocol/Study No: SC02 EMA/2018/19/PE

Page 26 of 92

patients with MTX experience to participate in the study. We used the unit volume of sales of MTX as a proxy to assess the prevalence of patients or eligible HCPs having experience with the drug (Table 2). Applying these criteria, we proposed the study to take place in the following 5 countries: France, Germany, Greece, Poland, and Sweden. Although, Italy was initially proposed in the proposal, it was replaced by Greece because of a lengthy regulatory and ethics process. If the target sample size is not achieved in one of the selected countries, the possibility of selecting an alternative country will be explored.

Table 2 The Proportions of Methotrexate Sales in 2020 in the European Market\*

Countries	The proportions of methotrexate sale	Selected for the study
Austria	1.0 %	
Belgium	5.6%	
Bosnia	0.4%	
Bulgaria	0.7%	
Croatia	1.1%	
Czech Republic	3.5%	
Estonia	0.7%	
Finland	2.1%	
France	11.2%	X
Germany	10.9%	X
Greece	5.4%	X
Hungary	2.2%	
Ireland	2.9%	
Italy	7.0%	
Latvia	0.3%	
Lithuania	0.3%	
Luxembourg	0.1%	
Netherlands	0.5%	

Template No.: RWI\_TP\_EPI0016 Revision 1 Reference: RWI\_WI\_EPI0005

Protocol/Study No: SC02 EMA/2018/19/PE

Page 27 of 92

Countries	The proportions of methotrexate sale	Selected for the study
Norway	3.6%	
Poland	10.6%	X
Portugal	4.2%	
Romania	0.5%	
Serbia	2.0%	
Slovakia	1.2%	
Slovenia	0.4%	
Spain	13.4%	
Sweden	7.0%	X
Switzerland	0.9%	
Total	100.0%	

\*The relative proportion of sales in European countries was obtained from IQVIA Midas. The denominator for all proportions is the total unit volume of sales of MTX products in the European countries presented in Table 2.

#### 9.2.1 Participant selection

#### 9.2.1.1 Prescriber Selection

Choice of the specialties to include in the survey will be based on the specialties that have been targeted for distribution of the DHPC and educational material (EM) by the relevant national competent authorities in the selected countries, for e.g. specialists including GPs, internists, rheumatologists, dermatologists, gastroenterologists etc. The choice of specialties can be variable between countries. To the extent possible, prescribing patterns will be obtained from IQVIA data assets as supportive evidence to document the choice of specialties. Please refer to Annex 2. List of Healthcare Professionals for a complete list of prescribers who received the DHPC/EMs per country.

In the absence of comprehensive lists of MTX prescribers, the initial sampling frame for the identification of participating prescribers will be based on the list of all prescribers (OneKey, IQVIA, OneKey is an IQVIA managed database with information of health care professionals) in each of the relevant specialties in the targeted country. OneKey databases are constructed and updated through manual and automated means from various sources, including publicly available sources. OneKey is the most comprehensive list of HCPs in the

Template No.: RWI\_TP\_EPI0016 Revision 1 Reference: RWI\_WI\_EPI0005

Protocol/Study No: SC02 EMA/2018/19/PE

Page 28 of 92

world with very high coverage in most countries (33). Also, in EU PAS Register, it can be seen where OneKey database has been used for other post-authorisation safety studies (PASS) such as EUPAS34465 and EUPAS32142.

Since the study objective is to determine the extent of prescriber awareness and knowledge of the risk of inadvertent overdose due to daily instead of weekly use of MTX, only prescribers who have prescribed in indications requiring once-weekly MTX (in the past 3 months) will be selected. As this information is not available in the lists of prescribers, the survey will be preceded by a set of questions to check the eligibility of prescribers. Among these, it will be asked if the prescriber has prescribed in indications requiring once-weekly MTX in the past 3 months. If the answer is no, the survey will not be administered to that prescriber.

Prescribers will be identified randomly from OneKey lists (IQVIA) which is representative of the target population in all of the countries and specialties. In case the number of prescribers is limited in a country, an invitation will be sent to all of them.

